1. H&P
2. Fasting labs: IGF-I, glucose, AST, ALT, GGT, total bilirubin, direct bilirubin, alkaline phosphatase, albumin, lipid panel, CBC, PT/INR, HbA1c, frozen serum for adiponectin, IL-6, CRP, CK18, and other relevant inflammatory biomarkers, as guided by the histological results
3. Height, metabolic weight, anthropometrics
4. Whole body DXA scan for regional fat
5. 24-hour Food Recall and Modifiable Activity Questionnaire by CRC bionutrition
6. Transient elastography (FibroScan)
7. Liver biopsy. Biopsy will not be done if performed in the 12 months prior to baseline and, in the interval since biopsy, no new treatment initiated and no weight change $>10\%$
8. Stable isotopes for assessment of hepatic de novo lipogenesis
9. Coronary CT angiography (CCTA) performed in individuals who meet the following criteria: BMI $<40\text{kg}/\text{m}^2$, age $\geq 40\text{y}$ for Males or $\geq 50\text{y}$ for Females. Individuals with any of the criteria detailed in "Exclusion Criteria (#22)" above will not undergo CCTA.
10. Peripheral blood mononuclear cells (PBMCs) will be processed for flow cytometry of immune cells and related immune studies at baseline and 12 months, as well as processed and stored for DNA at baseline.

Start of Study Drug

At the conclusion of the baseline visit, subjects will be instructed in reconstituting and administering tesamorelin or identical placebo, and they will self-administer their first injection at the conclusion of the visit. After administration, they will be observed for 30 minutes to ensure no allergic reaction.

Safety Visits (0.5, 1, 2, 3, 6, 9, 12.5, 15, months)

1. Interval H&P, weight
2. Fasting glucose, AST, ALT, GGT, albumin, alkaline phosphatase, total bilirubin, direct bilirubin, PT/INR, IGF-1
3. At 3, 6, 9, and 15 months, HbA1c
4. At 6 month visit only: ^1H -MRS/MRI of abdomen for quantification of liver fat and VAT, fibroscan, lipid panel

12 Month Visit

Identical to baseline visit except: ^1H -MRS/MRI of abdomen for quantification of liver fat and VAT will be performed; CCTA will not be performed. At the conclusion of the 12 Month Visit, subjects will self-administer

their first open-label injection, after which they will be observed for 30 minutes to ensure no allergic reaction.

18 Month Visit

1. Interval history, H&P
2. Fasting labs: glucose, IGF-I, AST, ALT, GGT, alkaline phosphatase, total bilirubin, lipid panel, HbA1c
3. Height, weight, anthropometrics
4. Whole body DXA scan for regional fat
5. 1H-MRS for quantification of liver fat, MRI of the abdomen for quantification of VAT
6. Transient elastography (FibroScan)
7. 24-hour Food Recall and Modifiable Activity Questionnaire by CRC bionutrition

Early Termination Visit

If a subject wants to discontinue the study, or if discontinuation is required due to an adverse event and/or one of the stopping rules, we may ask the subject to return for an Early Termination Visit that includes elements of the 18 month visit. This will be at the discretion of the Co-PIs and will be based on how much of the study the subject has already completed and which tests have already been performed.

Telephone Calls

In order to enhance subject retention, study staff or study physicians may call subjects periodically to ensure that study drug administration is going well and that they do not have any questions. Whenever possible, these calls will typically take place about midway between visits. Up to 6 of these phone calls may be made over 18 months.

Study Drug

The study drug is tesamorelin, a GHRH agonist (Theratechnologies, Inc., Montreal, Canada).

Tesamorelin is FDA approved for use in HIV-infected patients with visceral adiposity. Tesamorelin will be used in this study under an IND (#138045, Sponsor-Investigator [name]). The dose of tesamorelin is 1.4mg of F4 formulation subcutaneously daily, consistent with the FDA approved dose and equivalent to the dose used in prior studies.

IGF-1 levels will be checked at each visit and monitored by an independent physician not otherwise involved in the study. If a subject's IGF-1 z-score is ≥ 3 , this physician will instruct investigators to perform a dose reduction to 0.7mg daily, along with a dummy dose reduction in a placebo patient if the subject with elevated IGF-1 is in the double-blind phase of the study. IGF-1 will be rechecked in 1 month (window 3-5 weeks), following the dose reduction, and the subject will be discontinued from the study if z-score remains ≥ 3 . Subjects who are discontinued for persistent IGF-1 Z-score > 3 SD will be asked to come back in 1-2 months for a final IGF-1 recheck to ensure that it has normalized; if it has not normalized, the subject may have an underlying endocrine disease and will be referred to endocrinology.

Subjects who have symptoms that may be consistent with growth hormone excess, including myalgia, arthralgia, paresthesia, or edema, will be offered a dose decrease to 1mg daily or the option to discontinue the study. Subjects who opt for a dose reduction and still have these symptoms will be discontinued from the study if the investigator judges the symptoms to be greater than mild in nature.

With regard to injection site reactions, subjects will be informed to notify a study investigator of any sign of erythema, swelling, or pruritis. Subjects who notify us of such reactions will be asked to stop the study drug and come in for a supervised injection with a study investigator. If the reaction is not present during the supervised injection, and the subject feels comfortable continuing, s/he may restart drug with careful instructions to call again if they experience any erythema, swelling, or pruritis. Subjects with reports of these symptoms on two separate occasions, or any subjects with erythema and/or pruritis extending beyond the immediate injection site will be discontinued from the study. Subjects will be informed to seek emergency medical care immediately if they are experiencing any signs of allergic reaction such as hives, generalized urticaria, nausea, abdominal pain, vomiting, dizziness, syncope, difficulty breathing, incontinence, or general feeling of unwellness. Any subject who has any one of these symptoms in temporal combination with urticaria, redness, or swelling at the injection site will also be discontinued from the study.

Subjects with fasting glucose of > 126 mg/dL or HbA1c $> 6.5\%$ at any visit, confirmed by a re-draw, will be discontinued from the study. Although there are not plans to check random glucose levels, if any subject

has a random glucose level checked for other reasons that is ≥ 200 mg/dL, we will perform a fasting glucose. If this fasting glucose is ≥ 126 mg/dL, verified on repeat, this subject will be discontinued from the study.

Any subject with an evolving medical condition (e.g., progressive liver disease) such that continued participation in the study may incur risk or preclude appropriate clinical management will also be discontinued. Subjects with cirrhosis or decompensation during the trial will be discontinued. A physician or NP will be available 24/7 to subjects for any questions or concerns about the study drug.

Abnormal liver function tests will be managed per the algorithm below. If AST or ALT are ≥ 8 x ULN or 600 IU/L, we will ask patients to return within 1 week for CPK and LDH as needed for the algorithm.

Monitoring and Algorithm for Drug Induced Liver Injury

A. If isolated transaminase (AST or ALT) elevations are observed, defined as:

Normal bilirubin and absence of clinical hepatitis, AND

- ALT or AST ≥ 5 times the ULN if normal at baseline, OR
- ALT or AST ≥ 3 times the baseline or 400 U/L if abnormal at baseline

THEN

- Repeat liver profile (ALT, AST, bilirubin and PT/INR) within 2 to 3 days and
- Monitor the patient with laboratory testing and physical examination 2 to 3 times per week as per the “close observation” definition in the DILI guidance (<https://www.fda.gov/downloads/Drugs/.../Guidances/UCM174090.pdf>).
- We will be in close communication with the patient’s hepatologist and, if the abnormalities are thought to be related to study drug or do not have another reasonable explanation, we will permanently discontinue study drug

B. If any ONE of the following criteria is met:

- Transaminases (ALT or AST ≥ 3 x baseline) AND bilirubin (total bilirubin > 2 x ULN);
- Cholestatic markers (ALP or GGT > 2 x baseline);
- Isolated ALT/AST ≥ 8 x ULN or 600 U/L in presence of normal CPK and LDH and not secondary to cholangitis
- INR increase > 1.5
- OR: if any ONE of the following criteria is met for total bilirubin unrelated to hemolysis:
 - Doubling of total bilirubin
 - OR: any increase in total bilirubin if: there are symptoms of clinical hepatitis (e.g., vomiting, nausea, right upper quadrant pain)
 - OR: there are immunological reaction (rash or $> 5\%$ eosinophilia),

THEN

1. study medication will be permanently discontinued
2. a drug-induced liver injury workup must be initiated for alternate etiologies;
3. repeat liver profile (ALT, AST, total bilirubin, direct bilirubin, ALP) and PT/INR within 48 to 72 hours;
4. monitor the subject with further laboratory testing and physical examination 2 to 3 times per week as per the “close observation” definition in the DILI guidance (<https://www.fda.gov/downloads/Drugs/.../Guidances/UCM174090.pdf>).
5. If a subject lives in a remote area, they can be tested locally and the results communicated to the investigator promptly.
6. Subjects will be followed by the study investigator until changes are resolved or stabilized but will not come for further study visits apart from those related to safety monitoring of liver injury.

Individual stopping rules

Subjects will be discontinued from the study for any of the following:

- Fasting glucose > 126 mg/dL confirmed on a re-draw
- HbA1c $> 6.5\%$ confirmed on a re-draw if participant wishes
- IGF-1 Z-score persistently ≥ 3 after dose reduction
- Erythema or pruritis extending beyond the immediate injection site, indicating allergic reaction
- Pregnancy

- Development/diagnosis of active malignancy
- Significant symptoms of GH excess felt to be related to the study drug
- Clinical conditions, which in the best judgment of the investigator are believed to be harmful or potentially life-threatening to the participant, even if not felt to be related to the study drug and/or not addressed in the AE management section of the protocol.
- Request by participant to terminate study product(s)/intervention(s)

Because some of the follow-up study procedures, including liver biopsy and cardiac CT scan, have associated risks, there are no plans to continue following subjects who have discontinued study drug unless otherwise specified above, apart from the possibility of conducting an early termination visit as described above and/or ensuring return to baseline health for subjects who have had an adverse event.

Concomitant Medications

Concomitant medications will be documented at the screening visit and any change in medications will be carefully documented at each subsequent visit. All concomitant medications are allowed unless specifically prohibited in the eligibility criteria above. Given the possibility for growth hormone to affect CYP450, we have excluded patients receiving anticonvulsants or cyclosporine, as well as subjects who require corticosteroids for adrenal insufficiency. (Systemic corticosteroid use within 6 months of the study is also an exclusion criterion.) Subjects who are taking sex steroids or using other forms (e.g., topical) of corticosteroids will be warned that there may be an effect of the study drug to reduce the systemic concentration of these medications, and that we will speak with their prescribing physicians about this if requested.

Study stopping/pausing rules

- If one subject experiences a Grade 5 toxicity (based on National Cancer Institute Common Terminology Criteria for Adverse Events [NCI CTCAE] version 5), the trial will be paused and information will be submitted to the FDA for review. The trial will not be resumed without the okay from the FDA.
- If either of the following occurs, a special meeting of the DSMB will be convened within 2 weeks to determine if the trial may be continued. In this event, the trial will be continued pending DSMB review and determination:
 - More than 2 patients develop a CTCAE grade 3 or higher in the same category
 - More than 2 patients meet the individual stopping rules

Methods

¹H Magnetic Resonance Spectroscopy (MRS) & MRI: After at least 8-hour overnight fast subjects will undergo ¹H -MRS of the liver. A breath-hold true fast imaging with steady precession sequence will be obtained. ¹H -MRS data will be acquired using point-resolved spatially localized spectroscopy pulse sequence without water suppression. For abdominal visceral and subcutaneous fat volumes, conventional MR images will be acquired and will serve as anatomic reference of ¹H-MRS overlays. Proton density fat fraction will be calculated from integral lipid and water peak areas as previously described (88, 92).

Subjects undergoing MRI/MRS may develop claustrophobia during the scan. Patients will be queried regarding a history of claustrophobia and their ability to tolerate other MRIs during their screening history and phone screen. If they report prior claustrophobia or develop distress during the study MRI, they will be offered a low-dose benzodiazepine (1 mg lorazepam orally) at the time of their scan. Patients who receive anxiolytics will be monitored for a return to baseline mental status following the scan, and will be provided with a ride home.

Liver Biopsy: Percutaneous liver biopsy will be performed under ultrasound guidance using a 16-gauge needle by experienced interventional radiologists. Participants with any contraindication to liver biopsy, including platelets < 75,000, elevated PT or PTT, or chronic anticoagulation use will not undergo biopsy. Individuals on aspirin for primary prevention of CVD may undergo biopsy following discontinuation of aspirin for ≥5 days. One biopsy fragment will be fixed in 10% formalin for histopathological analysis. Histologic scoring will use validated scoring systems NASH Clinical Research Network scoring system (93) and Brunt Fibrosis staging. NASH will be defined by the presence of: steatosis ≥1, lobular inflammation ≥1 and hepatocyte ballooning ≥1. Steatosis will be defined the presence of steatosis grade ≥1, not meeting criteria for NASH.

Fibrosis stage will be scored from 0-4 following the Brunt staging system. A second fragment will be placed in an RNA stabilization reagent (RNAlater, Qiagen) for gene expression analysis. Following RNA extraction, tissue RNA will be subjected to Counter digital transcript counting (Nanostring) analysis in [name] laboratory using customized codesets and probes specifically designed for key inflammation, fibrosis, and metabolism-related genes. This technique has been used successfully by his group to perform expression analysis of specific gene sets in peripheral blood and liver tissue from large numbers of patients.

Contrast-Enhanced Coronary Computed Tomography Coronary Angiography (CCTA): This study is being performed in a subset of individuals in order to maximize image quality and the probability of finding plaque. Individuals with $BMI \geq 40 \text{ kg/m}^2$ will not have a scan because scan quality would be poor. Men $< 40 \text{ yo}$ and women $< 50 \text{ yo}$ will not be scanned because of the low likelihood of these individuals having plaque. Subjects must have a GFR of ≥ 60 for participation in the study. Participants on metformin will be asked to hold metformin 48 hours prior to CT scan as well as 48 hours after the scan. If the participant and/or his/her physician feel that holding metformin is not safe, the participant may participate in the study but will not have a the CT scan. Additional criteria for undergoing CCTA are detailed in Exclusion Criteria #22 above. Image acquisition will take place at MGH using a standardized protocol that employs several state-of-the-art technologies to minimize radiation dose (94). The CCTA protocol is based on the standard clinical CCTA protocol at MGH: Sublingual nitroglycerin (0.3-0.9 mg, typically 0.6 mg) will also be administered as per standard protocol for cardiac CT scans. The supervising physician will carefully screen for contraindications to this medication prior to administration. Prior to scans, subjects will be asked not to use medications for erectile dysfunction (e.g., Cialis, Viagra) for 3 days. A prospectively-ECG triggered noncontrast CT of the heart is obtained to measure coronary calcium. Contrast-enhanced CT acquisition will then take place. Based on subject size, 60-100 ml of nonionic iodinated contrast (iopamidol 370 g/cm³, Isovue 370, Bracco Diagnostics, Princeton, NJ) will be injected, followed by a flush of 40 ml of saline solution. After a delay based on the test bolus, a CT acquisition will be performed of the heart. A number of high-resolution images of the heart at slightly different time-positions within the cardiac cycle will be reconstructed, of which the best phase will be used to evaluate the coronary artery lumen, plaque distribution, and plaque morphology.

Stable Isotope Assessment of Hepatic DNL: Subjects will come to the CRC the evening before their baseline visit and will have 2 baseline samples drawn for baseline concentrations of stable isotope. Following this, they will consume 1g/kg of deuterated water along with a meal that contains caloric content equal to 40% of the estimated daily caloric needs ($\pm 100 \text{ kcal}$) based on the Mifflin-St. Joer Equation and macronutrient content as follows: 55% ($\pm 5\%$) carbohydrate, 30% ($\pm 5\%$) fat, and 15% ($\pm 5\%$) protein. Upon completion of the standardized meal, subjects will be discharged with a snack they can eat that evening, and otherwise will be instructed to remain fasting. They will arrive to the CRC in the morning following a 12-hour fast. Before breakfast, they will have fasting blood samples drawn at two timepoints, a few minutes apart, to assess deuterium incorporation into plasma TG-palmitate for calculation of fasting hepatic de novo lipogenesis. They will then have a standardized breakfast, with the same caloric and macronutrient content as the meal the night before. All water consumed by the subject until the completion of testing will contain 5g/L D₂O in order to maintain a plasma enrichment of 0.3%. Four hours after the standardized breakfast, at +230 and +240 minutes from completion of breakfast, blood samples will be drawn to assess post-prandial hepatic de novo lipogenesis. Use of deuterated water ingestion to measure enriched palmitate incorporation into triglyceride (TG) is now a well established method for assessment of hepatic DNL (95). Deuterated water will be obtained from Cambridge Isotope Laboratories, and assays for plasma TG-palmitate enrichment will be performed by [name] of Metabolic Solutions (Nashua, NH). Of note, subjects with body weight $\geq 100 \text{ kg}$ will be offered the option to skip the stable isotope testing because of the risk of side effects (see VI. Risks and Discomforts).

Transient Elastography: Liver stiffness will be determined using transient elastography (FibroScan®, Echosens, Paris, France) (96). Probe size (M or XL) will be selected based on the subject's body habitus, and the same probe will be used at all timepoints. At least ten measurements will be made and the median will be expressed in kilopascal (kPa) units.

Liver Ultrasound: A liver ultrasound ("Sonosite") may be used to determine the presence of fatty liver in

subjects without a known diagnosis. This will be performed by a trained technician and read by an experienced radiologist. This is not formally used for study eligibility but may be used to inform subjects that they do not seem to have fatty liver and may not want to undergo the remainder of screening procedures.

Whole Body DXA, Assessment of Nutrition and Activity: CRC bionutrition staff will perform the following assessments: Whole body DXA will be used to determine whole body and regional fat. The technique has a precision error (1 SD) of 3% for fat and 1.5% for lean body mass (97). 24-hour food recall will be administered to assess micronutrient and macronutrient intake, and Modifiable Activity Questionnaire (MAQ) will be administered to assess physical activity (98).

Medication adherence will be assessed by vial count and medication diary.

V. Biostatistical Analysis

Endpoints

Aim 1: Change in hepatic fat fraction as measured by ¹H-MRS after 1 year of randomized treatment (**Primary endpoint, Aim 1a**). Histological features of NASH, assessed by histopathological analysis of liver biopsy, including frequency of ≥ 2 point reduction in NAFLD activity score (NAS score) with no worsening of fibrosis stage and reduction in individual components of the NAS (**Aim 1b**).

Aim 2: Change in post-prandial hepatic DNL by stable isotope methods (**Aim 2a**). Change in mRNA expression of genes related to hepatic lipid metabolism in liver tissue obtained by biopsy. Target genes will include SCD1, FAS, SREBP1c, CD36, PPAR α , PPAR γ , CPT1, LDLR (**Aim 2b**). Change in mRNA expression of genes related to inflammation/oxidative stress and fibrosis/fibrogenesis in liver tissue. Target genes include: MCP1, TNF α , IL-1 β , IL-6, IL-18, TLR, MyD88, CCL5, TGF β 1, NF κ B, TIMP1, COL1A1, MMP 1-14 (**Aim 2c**). Exploratory endpoint: change in immune cell phenotypes assessed by flow cytometry

Aim 3: Change in circulating fasting lipids, c-reactive protein, tissue plasminogen activator antigen, plasminogen activator inhibitor-1 antigen, adiponectin, and potentially other circulating markers as guided by emerging science regarding noninvasive CVD risk measures (**Aim 3a**).

Supportive endpoints of interest include change in liver stiffness measured by fibroscan, change in AST, ALT, and GGT, and change in fasting glucose, insulin, and HOMA-IR.

Planned Data Analysis

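### CPK and LDH, which the automatic stop at isolated ALT/AST ≥ 8 × ULN or 600 U/L depends on, may be drawn up to a week later, although most or all of these patients must already return at 2 to 3 days

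*Combined protocol and SAP*

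**What the plan says.** The rules are in section IV, at the end of Study Drug and under Monitoring and Algorithm for Drug Induced Liver Injury.

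- **Recall for CPK and LDH.** When AST or ALT reaches 8 × ULN or 600 IU/L, "we will ask patients to return within 1 week for CPK and LDH as needed for the algorithm".
- **Part B, automatic permanent stop.** One of several criteria is an isolated ALT/AST at that level "in presence of normal CPK and LDH and not secondary to cholangitis". After the stop, part B asks the site to "repeat liver profile (ALT, AST, total bilirubin, direct bilirubin, ALP) and PT/INR within 48 to 72 hours".
- **Part A, lower elevations.** It opens with "If isolated transaminase (AST or ALT) elevations are observed, defined as" and then requires normal bilirubin, no clinical hepatitis, and a value of at least 5 × ULN (normal baseline) or at least "3 times the baseline or 400 U/L if abnormal at baseline". The action is "Repeat liver profile (ALT, AST, bilirubin and PT/INR) within 2 to 3 days", followed by "Monitor the patient with laboratory testing and physical examination 2 to 3 times per week".
- **Part A, stop.** It rests on a judgement of cause: "if the abnormalities are thought to be related to study drug or do not have another reasonable explanation, we will permanently discontinue study drug".

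The Safety Visits laboratory list and the liver panel footnote in Appendix 1 include neither CPK nor LDH. Dosing is once daily (Study Drug). The algorithm does not tell the site to withhold drug while the two results are pending.

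**The concern.** The higher transaminase level has the slower clock. A patient at 5 × ULN must be retested within 2 to 3 days. At 8 × ULN, the tests needed to apply the automatic stop may wait a week. No listed panel supplies them sooner, and a draw on day 7 complies fully with the protocol.

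The patient at risk is one whose elevation is provisionally put down to something other than study drug, so that part A's judgement-based stop is not used. Muscle is a plausible attribution, since Table 2 lists myalgia as a known side effect (6%). CPK and LDH are the tests part B uses to check for other explanations, so an earlier result would inform the part A decision too. A sample taken up to a week after the transaminase value may also no longer describe the same clinical state.

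**Working it through.** The plan gives no figure to reproduce. The check has two parts: whether patients at this level already attend at 2 to 3 days, and how much time the 1-week window adds.

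**1. Overlap with part A**

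Let V be the on-treatment ALT or AST, B the baseline value and U the upper limit of normal. The part B level is V ≥ 8U or V ≥ 600. Part A needs V ≥ 5U if baseline is normal, and V ≥ 3B or V ≥ 400 if abnormal, reading the *or* as either limb sufficing. The documents give no ULN, so U is varied as an assumption. The 600 U/L limb adds patients only when 8U > 600, that is U > 75.

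- *Normal baseline.* V ≥ 8U implies V ≥ 5U. V ≥ 600 implies V ≥ 5U whenever U ≤ 600/5 = 120. All such patients are in part A for any U up to 120 U/L.
- *Abnormal baseline, 600 U/L limb.* 600 > 400, so all are in part A.
- *Abnormal baseline, 8 × ULN limb.* If 8U ≥ 400, that is U ≥ 50, all are in part A. If U < 50, a patient is missed only when V < 400 and V < 3B. With V ≥ 8U this needs B > 8U/3 = 2.67U.

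| Assumed ULN (U/L) | V that could miss part A | Baseline needed (U/L) |
|---|---|---|
| 30 | 240 to < 400 | > 80 |
| 35 | 280 to < 400 | > 93.3 |
| 40 | 320 to < 400 | > 106.7 |
| 45 | 360 to < 400 | > 120 |
| 50 or more | none | – |

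A grid search over baseline and on-treatment values gave the same boundaries. The gap exists only if *isolated* in part B does not carry over part A's definition. If the whole definition carries over, thresholds included, the gap is empty at every ULN. Hence *most or all*.

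Patients with raised bilirubin or clinical hepatitis fall outside part A, but they may meet other part B criteria that need neither CPK nor LDH.

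**2. Time and doses**

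- Latest compliant draw: day 7.
- Part A repeat: day 2 to 3, equal to 48 to 72 hours.
- Difference: 7 − 3 = 4 days to 7 − 2 = 5 days.
- At one dose per day: 4 to 5 doses.

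Laboratory turnaround adds equally to both routes and cancels. During those 7 days part A monitoring already means 2 to 3 laboratory contacts.

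**The case against.** The strongest reply is that nothing conflicts. One week is a maximum, a draw at 2 to 3 days satisfies it, and staff can add two tubes to the part A visit. Part A also requires a permanent stop for an elevation judged drug-related or unexplained, without waiting for either test, and Study Drug and Individual stopping rules add further judgement-based stops. For the delay to matter, another explanation must be accepted, CPK and LDH must then prove normal, cholangitis must be excluded, no other part B criterion may be met, and the draw must be left late. If CPK proves raised, this criterion never applies and no stop was delayed. In the double-blind phase some of the doses are placebo.

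Most of this stands and sets the size of the point. Three further limits also stand:

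- The 48 to 72 hour repeat in part B follows a stop already made, so the part A repeat is the proper comparator.
- The analytes in the close-observation guidance cited by part A are not visible in these documents. The omission is established only for the named repeat profile.
- Section VI reports no clinically significant ALT or AST changes in earlier studies of the drug. Those were in HIV, whereas this trial selects for fatty liver, but few cases should still be expected.

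What does not stand is that the upper limit is harmless because sites may act sooner. A safety window is judged by what it permits, and the visible text does not require the earlier draw.

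**Conclusion.** The concern holds, as a timing mismatch and not a contradiction. Tests required for one automatic stop may be drawn 4 to 5 days after a visit that most or all of the same patients must already attend, with up to 4 to 5 daily doses in between. That count is a worst case: it assumes the part A stop is not used and the draw falls on day 7. *All* rather than *most* depends on a ULN of at least 50 U/L, or on part A's full definition of isolated elevation applying in part B. The documents give no frequency. Severity is minor: the point bears on participant safety and has no effect on the primary endpoint, power or type I error.

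**What to change.** Make two wording changes in the liver injury algorithm:

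1. In the recall sentence, replace the 1-week limit with 48 to 72 hours, or have CPK and LDH measured on the index sample whenever ALT or AST is at least 8 × ULN or 600 U/L.
2. In the part A repeat profile, add CPK and LDH for patients at that level if not already measured.

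A sentence on dosing while results are pending could be added, but the point does not depend on it.

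The cost is two protocol phrases and two assays at a draw already required for most or all of these patients. Local testing is already provided for under Remote Visits and in part B. No endpoint, sample size or analysis changes.

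### Liver-injury algorithm: a Part A-level ALT/AST rise with mildly raised bilirubin, or with hepatitis symptoms and no bilirubin rise, can meet neither Part A nor Part B

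*Combined protocol and SAP*

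**What the plan says.** Section IV, Study Drug, introduces the algorithm with "Abnormal liver function tests will be managed per the algorithm below". The algorithm has two branches.

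- **Part A** covers isolated transaminase elevations. Its entry condition is "Normal bilirubin and absence of clinical hepatitis, AND" either ALT/AST at least 5 x ULN (normal baseline), or at least 3 x baseline or 400 U/L (abnormal baseline). Its first action is "Repeat liver profile (ALT, AST, bilirubin and PT/INR) within 2 to 3 days and" laboratory tests and examination two to three times a week. The team also contacts the hepatologist, and stops the drug for good if the abnormality seems drug-related or has no other reasonable explanation.
- **Part B** needs any one of these: ALT/AST at least 3 x baseline with total bilirubin above 2 x ULN; ALP or GGT above 2 x baseline; isolated ALT/AST at least 8 x ULN or 600 U/L, "in presence of normal CPK and LDH and not secondary to cholangitis"; an INR increase above 1.5; a doubling of bilirubin; "any increase in total bilirubin if: there are symptoms of clinical hepatitis"; or an immunological reaction. Its actions are permanent discontinuation, a full work-up, repeat tests in 48 to 72 hours and close observation.

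There is no third branch.

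**The concern.** Two branches that are meant to manage abnormal liver tests should between them cover every elevation that reaches the lower threshold. Here Part A excludes anyone with raised bilirubin or clinical hepatitis, and Part B takes back only some of those patients. The rest have ALT/AST high enough for Part A but no mandated repeat, observation or work-up.

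Where bilirubin has newly risen, or symptoms have appeared, the written rule then guarantees less monitoring than it does for a patient with the same ALT/AST, normal bilirubin and no symptoms. What is at stake is participant safety and consistent handling of liver signals. The efficacy analysis is not involved.

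**Working it through.** **Inputs.** All criteria come from the algorithm in section IV. Values are in multiples of ULN. The documents give no ULN for ALT, so where the U/L limits matter I assume 30 to 60 U/L. I read a rise or a doubling of bilirubin as measured from baseline. ALP/GGT, INR and immunological triggers are taken as absent, and ALT/AST as below 8 x ULN and 600 U/L.

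**Step 1: what is left of Part B.** Three criteria remain: (i) ALT/AST at least 3 x baseline and bilirubin above 2 x ULN; (ii) bilirubin doubled; (iii) any bilirubin rise together with hepatitis symptoms.

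**Step 2: who fails Part A and also (i) to (iii).**

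- (a) Bilirubin above normal, not doubled, no symptoms, (i) unmet.
- (b) Clinical hepatitis, bilirubin not risen, (i) unmet. Symptoms rule out Part A, but criterion (iii) needs a rise as well.

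**Step 3: worked patients.**

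| ALT, baseline to now | Bilirubin, baseline to now | Symptoms | Result |
|---|---|---|---|
| 0.8 to 6 | 0.8 to 0.8 | no | Part A |
| 0.8 to 6 | 0.8 to 1.5 | no | Neither (1.5 < 2 × 0.8 = 1.6) |
| 0.8 to 6 | 0.8 to 1.5 | yes | Part B, rise with symptoms |
| 0.8 to 6 | 0.8 to 1.6 | no | Part B, doubling |
| 0.8 to 6 | 0.5 to 0.5 | yes | Neither |
| 0.8 to 6 | 0.5 to 0.55 | yes | Part B, rise with symptoms |
| 1.5 to 7 | 1.3 to 1.9 | no | Neither (7/1.5 = 4.67; 1.9 < 2.6 and not above 2) |
| 1.5 to 7 | 1.3 to 1.3 | no | Neither, bilirubin stable |
| 1.5 to 7 | 0.8 to 2.1 | no | Part B, doubling and combined criterion |

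**Step 4: width of the window.**

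- *ALT.* From 5 to below 8 with a normal baseline. With an abnormal baseline it starts at 3 x baseline: 3.6 at baseline 1.2, 4.5 at 1.5, 6 at 2.0 and 7.5 at 2.5, each to below 8. It closes at baseline 8/3 = 2.67 if the ULN is 50 U/L or less. Above 50 U/L, the 400 U/L arm of Part A lies below 8 x ULN and a window stays open: from 400/55 = 7.27 at ULN 55, or 400/60 = 6.67 at ULN 60.
- *Bilirubin in case (a), with ALT/AST at least 3 x baseline.* Above 1.0 and below twice baseline, and no higher than 2.0. This is empty at baseline 0.5 or lower. It is above 1.0 to below 1.2 at baseline 0.6, to below 1.6 at 0.8, to below 2.0 at 1.0, and up to 2.0 at 1.1 or higher.

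**Step 5: two corners that fix the exact wording.**

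- Bilirubin above 2 x ULN does not always lead to Part B. Take ULN 55 U/L, baseline ALT 150, ALT now 410. This is above 400, below 8 × 55 = 440, and 410/150 = 2.73 x baseline. With bilirubin from 1.2 to 2.2 x ULN (ratio 1.83) and no symptoms, neither part applies.
- Clinical hepatitis with unchanged bilirubin does not always miss Part B. If bilirubin was already above 2 x ULN and ALT/AST is at least 3 x baseline, criterion (i) is met.

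**Step 6: what remains if nobody acts on judgement.** From the visit list in section IV, the next scheduled panel is 0.5 to 1 month away up to month 3, 3 months between months 3 and 12, 0.5 month to 12.5, 2.5 months to 15, and 3 months to 18.

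**The case against.** The strongest reply is that the algorithm does not stand alone.

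- Section IV, Study Drug, makes discontinuation mandatory once participation may incur risk: "Any subject with an evolving medical condition (e.g., progressive liver disease" is how that clause opens.
- The individual stopping rules likewise require discontinuation for conditions the investigator judges harmful, even where the adverse event section does not address them.
- Participants have a clinician on call at all hours. "Subjects will be informed to seek emergency medical care immediately" covers nausea, vomiting and abdominal pain, although it is framed around allergic reaction.
- Section XI counts an abnormal laboratory result as an adverse event, has the principal investigators review events in real time, and puts hepatology expertise on the DSMB. More than two grade 3 or higher events in one category trigger a special DSMB meeting within 2 weeks.
- Recruitment is mainly from a NAFLD cohort and a fatty liver clinic in which study personnel are involved.
- Section VI reports no clinically significant ALT/AST changes in earlier studies, though the large ones it describes were in people with HIV.

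All of this stands as a limit on severity. A reader might infer that symptomatic patients would go unmanaged, and these provisions do not support that. They do not close the gap either: each depends on someone judging the case or reporting an event, none sets a timed repeat panel or close observation, and the individual stopping rules contain no liver-test threshold.

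A reader might also infer that monitoring falls as disease worsens for everyone left out. That is too strong. A patient whose bilirubin was raised at entry and has not moved (the eligibility criteria state no bilirubin limit) is also left out, but that bilirubin shows no worsening on the drug. The inversion holds for a new rise or for symptoms.

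**Conclusion.** Wrong as written, but a minor correction to a safety rule. Within the ALT/AST window above, cases (a) and (b) meet neither part, and this follows from the wording alone. It rests on reading bilirubin changes against baseline and on the absence of the other Part B triggers. The assumed ULN affects only the U/L arms.

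The documents give no basis for saying how often such patients will occur. Few are expected and harm is unlikely. The primary endpoint and its analysis are not affected. The defect lies in what the rule guarantees: a timed repeat and close observation for the milder picture, and neither for some patients with a new bilirubin rise or with symptoms.

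**What to change.** Apply Part A's actions to every ALT/AST elevation that reaches a Part A threshold and does not meet Part B, whatever the bilirubin or symptoms. The actions stay as they are: repeat panel in 2 to 3 days, observation two to three times a week, hepatologist contact, and discontinuation if drug-related or otherwise unexplained. Every patient marked as neither in the table then falls under Part A, as does the patient with ULN 55 U/L. Those already in Part A or Part B stay there.

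Leave Part B unchanged, including the word *isolated* in the 8 x ULN line. If that word carries Part A's meaning, deleting it would move patients with very high ALT/AST and mildly raised bilirubin into automatic permanent discontinuation. That is a separate decision.

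The cost is a reworded entry condition in a protocol amendment and a few more recalls for laboratory tests and examination. It adds no automatic drug stop, because stopping under Part A remains a judgement.
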